### Secondary objectives

- a) Estimate the incidence rate of hospitalization due to CAP among COPD patients who were treated with Trelegy 100 or MITT. Overall, or incident triple use patients will be analysed in Trelegy 100 group and MITT group, respectively.
- b) Describe characteristics of COPD patients who were treated with Trelegy 100 or MITT. Overall, or incident triple use patients will be analysed in Trelegy 100 group and MITT group, respectively.
- c) Calculate crude and adjusted HRs for hospitalization due to CAP within Trelegy 100 or MITT group for each covariate, with one of the covariate subgroups serving as the reference group. Each model would be adjusted for all the other stated covariates. Overall, or incident triple use patients will be analysed in Trelegy 100 group and MITT group, respectively.  
In the model, following subgroups will be considered;  
gender, age, calendar year of Index date, month of Index date, COPD treatments in look-back period, hospitalization due to COPD exacerbation in look-back period, hospitalization due to CAP in look-back period, comorbidities of pre-defined disease such as asthma, myocardial infarction, congestive heart failure, cerebrovascular disease, dementia, peptic ulcer, peripheral vascular disease, connective tissue disease, diabetes, anxiety, depression, body mass index (BMI), smoking history, and execution of lung function test within Trelegy 100 or MITT group.
- d) Describe change over time in the expansion of triple therapy, use of an ICS-containing medications, and proportion of asthma comorbidity among COPD patients. Over-time refers to 360 days prior to date of launch of Trelegy 100, and 0-359 days, 360-719 days, 720- 1079 days after the launch. Target population for this objective includes COPD patients regardless of treatment.  
\*Overall users refer to those have prescriptions of Trelegy 100 or MITT between May 22, 2019 (launch date of Trelegy 100) and May 5, 2022. The index date will be the first prescription date on or after May 22, 2019.

Incident users are subpopulation of overall users who do not have any triple therapies for 360 days before the index date.

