### 8.3.3. Confounders and effect modifiers

#### 8.3.3.1. Covariates

The following covariates data will be used to calculate the marginal HR for hospitalization due to CAP among incident Trelegy 100 users compared to incident MITT users (primary objective), to characterize target patients (secondary objective-b) and to calculate adjusted HRs for “hospitalization due to CAP” among subgroups within Trelegy 100 or MITT groups (secondary objective-c)).

- **Sex**
- **Age:** Age at index date
- **Calendar year of index date:** Because medical practice changes over time
- **Month of index date (and not the month of hospitalization due to CAP):** Because of seasonal differences in pneumonia occurrence
- **COPD treatments in look-back period**
  - 1) Immediate previous treatment as COPD maintenance therapy (LAMA, LABA, LAMA/LABA, ICS/LABA, ICS/LAMA/LABA or no COPD maintenance therapy): As potential confounding factors
    - Immediate previous therapy will be identified during 180 days before the index date (and not during the entire look-back period).
  - 2) Prescriptions of ICS as treatment of COPD or asthma: As a risk factor for pneumonia occurrence during the look-back period  
Confirm that ICD-10 code for COPD (J42, J43 or J44) or asthma (J45 or J46) is recorded in the receipt of the month which includes prescription of ICS.
  - 3) Prescriptions of oral corticosteroid (OCS) as treatment of COPD or asthma: As a risk factor for pneumonia occurrence during the look-back period  
Confirm that ICD-10 code for COPD (J42, J43 or J44) or asthma (J45 or J46) is recorded in the receipt of the month which includes prescription of OCS.
  - 4) Home oxygen therapy (HOT) for COPD: As an index for COPD severity  
Confirm that ICD-10 code for COPD (J42, J43 or J44) is recorded in the receipt of the month which includes the conduct of HOT.
    - Other therapies (including rescue therapy, xanthine, biologicals) for COPD or asthma will not be included as covariates.

- **History of COPD exacerbation**

In MDV database, hospitalization due to COPD exacerbation (severe COPD exacerbation) will be identified correctly by using DPC data, while it is difficult to identify mild/moderate COPD exacerbation without hospitalization (i.e., without DPC data) because systemic corticosteroids/antibiotics are prescribed for various diseases and prescription data are not linked with disease data one by one.

Hospitalizations due to COPD exacerbation in the look-back period.

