- Definition: Hospitalization due to COPD exacerbation in the look-back period will be identified using DPC data. The following ICD-10 codes, DPC disease classification codes and prescription data will be used.
  - 1) Any of the following ICD-10 codes as DPC disease segment #21 (disease which triggered the hospitalization)
    - Pneumonia-related codes: J10.0, J11.0, J12-J18
    - Acute lower respiratory tract infection-related codes: J20-J22
    - COPD exacerbation-related codes: J44.1
    - Chronic respiratory failure: J96.1
  - 2) Prescription of any systemic corticosteroid combined with any systemic antibiotics at the admission day or the next day. Date of prescription with systemic corticosteroid can be the same as or different from that of antibiotics prescription.

If both of the above 1) and 2) are recorded on the same hospitalization, it is defined as “COPD exacerbation requiring hospitalization”.

Only the presence or absence of the event in the look-back period will be identified.

- **History of pneumonia**

Hospitalization due to CAP in the look-back period

- Definition: Same definition as the outcome measure (see “Sec 8.3.2 Outcome definitions”)
- Only the presence or absence of the event n look-back period will be identified.

■ **Medical history or comorbidities**

The following medical history or comorbidities in the look-back period

- Definition:  $\geq 1$  record (outpatient visit or hospital admission) with relevant ICD-10 codes for each comorbidities in the look-back period [Index date – 360 days]
  - 1) Asthma (ICD-10 codes: J45, J46)
  - 2) Myocardial infarction (ICD-10 codes: I21.x, I22.x, I25.2)
  - 3) Congestive heart failure (ICD-10 codes: I09.9, I11.0, I13.0, I13.2, I25.5, I42.0, I42.5-I42.9, I43.x, I50.x, P29.0)
  - 4) Cerebrovascular disease (ICD-10 codes: G45.x, G46.x, H34.0, I60.x-I69.x)
  - 5) Dementia (ICD-10 codes: F00.x-F03.x, F05.1, G30.x, G31.1)
  - 6) Peptic ulcer (ICD-10 codes: K25.x-K28.x)
  - 7) Peripheral vascular disease (ICD-10 codes: I70.x, I71.x, I73.1, I73.8, I73.9, I77.1, I79.0, I79.2, K55.1, K55.8, K55.9, Z95.8, Z95.9)
  - 8) Connective tissue disease (ICD-10 codes: M05–M08, M30–M36)
  - 9) Diabetes (ICD-10 codes: E10.0-E10.9, E11.0-E11.9, E12.0-E12.9, E13.0-E13.9, E14.0-E14.9)
  - 10) Anxiety (ICD-10 codes: F40-F42)
  - 11) Depression (ICD-10 codes: F32, F33)

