- Data of medical history/comorbidity of asthma will be collected by the definition using both ICD-10 codes and prescription data, in addition to the definition using only ICD-10 codes.

Definition:  $\geq 1$  records of visits (outpatient visit or hospital admission) with ICD-10 codes (J45, J46) and  $\geq 1$  records of prescriptions of at least one of ICS, ICS/LABA or leukotriene receptor antagonist (LTRA)

■ **BMI**

BMI will be calculated by body weight and height. Data of body weight and height are available from hospitalization records (DPC data or medical receipt data). If a study participant is hospitalized by any reasons in the look-back period, BMI data can be available from the hospitalization record.

■ **Smoking history**

Smoking history data are available from hospitalization records (DPC data or medical receipt data). If a study participant is hospitalized by any reasons in the look-back period, smoking history data can be available from the hospitalization record.

■ **Lung function test**

Presence or absence of lung function test in the look-back period. Lung function test results are not available but Yes/No of conducting lung function test are recorded in MDV database.

The following covariates have been considered in previous studies which had evaluated the association between ICS treatment and pneumonia occurrence among COPD patients. These covariates are baseline characteristics of study population and a certain length of time close to the period with exposure (Trelegy 100 or MITT) will be needed to collect data. Therefore we will collect these covariate data in the 360 days before the index date (look-back period).

■ **COPD treatments in the look-back period**

- 1) Immediate previous treatment as COPD maintenance therapy (LAMA, LABA, LAMA/LABA, ICS/LABA, ICS/LAMA/LABA or no COPD maintenance therapy)
- 2) Prescriptions of ICS as treatment of COPD or asthma: As a risk factor for pneumonia occurrence
- 3) Prescriptions of OCS as treatment of COPD or asthma: As a risk factor for pneumonia occurrence

- History of COPD exacerbation
- History of pneumonia
- Medical history or comorbidities
  - 1) Asthma
  - 2) Myocardial infarction
  - 3) Congestive heart failure
  - 4) Cerebrovascular disease
  - 5) Dementia

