#### **8.7.3.2.6. Change over time in the proportion of triple therapy among COPD patients**

The status of COPD maintenance therapy for COPD patients will be counted for each year, and the proportion of COPD maintenance therapy based on the number of COPD patients will be calculated. In addition, the details of triple therapy will be calculated. The change over time in the proportion of any ICS-containing therapies and comorbid asthma among COPD patients will be calculated. Over-time refers to 360 days prior to date of launch of Trelegy 100, and 0-359 days, 360-719 days, 720- 1079 days after the launch. Target population for this objective includes COPD patients regardless of treatment.

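### The code-plus-prescription asthma definition leaves out single-inhaler ICS/LAMA/LABA, so if it is used for the asthma trend in secondary objective d) the post-launch proportions are biased downward

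*Protocol*

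**What the plan says.** Section 8.3.3.1 lists asthma among the comorbidities by code alone: "Asthma (ICD-10 codes: J45, J46"). It then adds a second measure, which needs at least one visit with J45 or J46 and also "records of prescriptions of at least one of ICS, ICS/LABA or leukotriene receptor antagonist (LTRA"). This second measure is collected "in addition to the definition using only ICD-10 codes", so the two run in parallel.

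Earlier in the same section, the covariate for immediate previous maintenance treatment has these categories: "LAMA, LABA, LAMA/LABA, ICS/LABA, ICS/LAMA/LABA or no COPD maintenance therapy". ICS/LAMA/LABA is therefore a class of its own in this protocol.

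Secondary objective d) in section 7 is to "Describe change over time in the expansion of triple therapy, use of an ICS-containing medications, and proportion of asthma comorbidity among COPD patients". Section 8.7.3.2.6 repeats it: "The change over time in the proportion of any ICS-containing therapies and comorbid asthma among COPD patients will be calculated". The windows are fixed there: "Over-time refers to 360 days prior to date of launch of Trelegy 100, and 0-359 days, 360-719 days, 720- 1079 days after the launch". Neither place says which asthma definition is meant. Section 8.3.1 adds that single-inhaler triples other than Trelegy 100 count for objective d) only.

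**The concern.** The omitted class is the one whose spread objective d) is meant to describe. A patient with an asthma code who moves from ICS/LABA plus LAMA to Trelegy 100 alone has the same disease and still inhales a steroid, yet stops meeting the second definition once a whole window passes with no separate ICS, ICS/LABA or LTRA prescription. No patient can be in that position because of Trelegy 100 before its launch; after launch such patients can accumulate. The error therefore has one direction and is tied to the exposure.

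At stake is the reading of a descriptive result. Objective d) sets triple therapy, ICS use and asthma side by side over time, and an artificial decline in asthma while triple therapy grows would invite a wrong explanation.

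**Working it through.** The protocol states no figure for this quantity, so there is nothing to reproduce. The check is a reading of the text followed by an illustration.

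**Step 1. Does ICS in the list cover a single-inhaler triple?** If ICS meant any product containing a steroid, naming ICS/LABA beside it would be redundant. Where the protocol means the whole family, in objective d), it speaks of ICS-containing treatment. The natural reading is ICS alone, ICS/LABA, or LTRA.

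**Step 2. Apply the rule to one window.** All patients have a J45/J46 code and no LTRA.

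| Inhaled treatment throughout the window | Code only | Code plus prescription |
|---|---|---|
| ICS/LABA + LAMA | asthma | asthma |
| LAMA/LABA + ICS | asthma | asthma |
| Trelegy 100 or another single-inhaler triple only | asthma | not asthma |
| Switch from ICS/LABA + LAMA to Trelegy 100 within the window | asthma | asthma |

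The last row assumes that prescriptions are counted per window.

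**Step 3. Dates.** From 22 May 2019 to 5 May 2022 is 1,080 days. The post-launch windows run from 22 May 2019 to 15 May 2020, from 16 May 2020 to 10 May 2021, and from 11 May 2021 to 5 May 2022. The fourth window lies wholly before launch, so its loss from Trelegy 100 is zero.

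**Step 4. Illustrative size.** Let P be the proportion that would meet the definition if ICS/LAMA/LABA counted, s the share of those patients whose only ICS in the window is a single-inhaler triple, and k the share of that group who still qualify through LTRA. Then

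measured proportion = P × (1 − s × (1 − k)).

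All three inputs are assumptions. With P = 30%:

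| s | k = 0 | k = 0.6 |
|---|---|---|
| 5% | 28.5% | 29.4% |
| 10% | 27.0% | 28.8% |
| 30% | 21.0% | 26.4% |

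The shortfall runs from 30 − 29.4 = 0.6 to 30 − 21.0 = 9.0 percentage points. Under the code-only definition it is 0 for any s, and with ICS/LAMA/LABA in the list it is also 0.

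A second route to s uses the one related figure in the protocol, the forecast in section 8.5: 6450 / (6450 + 4370) = 0.596. Take s = T × 0.596 × a, where T is the share of asthma-coded patients on triple therapy and a is the share of Trelegy users with no separate ICS or ICS/LABA in the window.

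- T = 0.3 to 0.5, a = 0.7 to 0.9, k = 0.2 to 0.5: the relative loss s × (1 − k) runs from 0.3 × 0.596 × 0.7 × 0.5 = 6% to 0.5 × 0.596 × 0.9 × 0.8 = 21%.
- T = 0.2 with the same a and k: 4% to 9%.

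T, a and k are again assumed. The 0.596 is a forecast of users over the whole identification period, not a share of asthma-coded patients in any one window.

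**Step 5. Primary analysis.** Incident users have no triple therapy in the look-back, so the omission cannot change their look-back status. For overall users, the index date is the first Trelegy 100 or MITT prescription from launch onward, so no Trelegy 100 precedes it; only another single-inhaler triple could. This relies on covariates being measured before the index date, as section 8.3.3.1 says. Sections 8.1 and 8.2.1 write the look-back interval with the index date as its endpoint. If index-day prescriptions counted, MITT starters could qualify through their index ICS or ICS/LABA and Trelegy starters could not.

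**The case against.** The strongest reply is that the protocol does not tie this definition to objective d). Section 8.3.3.1 gives the uses of its covariates as the primary hazard ratio, then "to characterize target patients (secondary objective-b) and to calculate adjusted HRs" within groups (objective c). Objective d) is not named, and it covers COPD patients regardless of treatment, many of whom have no index date or look-back. How asthma is counted there may properly be left to the statistical analysis plan. This stands, and it makes the bias conditional. It does not remove the point: section 8.3.3.1 holds the protocol's only asthma definitions, so objective d) has to borrow one of them or bring in a new one.

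A second reply is that the omission may be deliberate. The prescription condition adds specificity for asthma and cites an asthma guideline, while the protocol gives Trelegy 100's indication as COPD. The guideline is not at hand, so intent cannot be excluded. But the list does not separate asthma treatment from COPD treatment: ICS/LABA counts, although the same section lists it as COPD maintenance therapy. An MITT patient on ICS/LABA plus LAMA is confirmed by exactly the kind of prescription that is refused for Trelegy 100.

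A third reply is that the code-only measure is planned anyway and, if both were reported, a divergence would be visible. That is right, and it limits the harm.

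**Conclusion.** The point holds in a limited form. The prescription list omits ICS/LAMA/LABA, and the resulting misclassification runs one way and follows the exposure. If this definition is used for objective d), the asthma proportion is understated in the post-launch windows. The size cannot be found from the document; 0.6 to 9.0 points at P = 30% is an illustration on assumed inputs.

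A reader might infer more, and the document does not support it:

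- That these patients lose their asthma status altogether. The code-only definition keeps it, and so does one ICS, ICS/LABA or LTRA prescription in the window.
- That the reported trend must fall. The definition for objective d) is open, and true prevalence may move either way; only the direction of the bias is fixed.
- That a fall would show triple therapy spreading to patients without asthma. The measure is asthma among all COPD patients, not among triple users.
- That the primary hazard ratio is compromised. It is essentially unaffected, given a look-back that ends before the index date.

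Severity is minor: one descriptive secondary objective.

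**What to change.** In section 8.3.3.1, change the prescription condition to at least one of ICS, ICS/LABA, ICS/LAMA/LABA (any single-inhaler triple) or LTRA, and apply it wherever this covariate is used. In section 8.7.3.2.6, state that the asthma proportion uses either this amended definition or the code-only one, and the same one in all four windows. If the class is left out on purpose, say so and use the code-only measure for the trend.

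The cost is one protocol line on each of the two points and one drug class in the code list. No new data are needed, and the primary analysis does not change.

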### 8.3.3.2. Other variables

The variable below will be included only in the table confirming patient characteristics.

- **Length of follow-up period:** To confirm the difference between Trelegy 100 and MITT groups.

## 8.4. Data Sources

The proposed study will be conducted using the Japanese MDV hospital claims database. MDV is a Japanese company specializing in integrated medical systems that manages a large administrative database constructed from hospitals (mainly tertiary) in Japan. The MDV data cover around 25% of acute care hospitals in Japan (439 hospitals) and include both inpatient and outpatient services. For the cumulative period between April 2008 and February 2021, the database has over 35.7 million patients, making it one of the largest Japanese healthcare datasets.

This study will use all available data between November 2017 and Apr 2023 in the MDV hospital claims database to assess the proposed study objectives. The data is updated monthly, thereby minimizing the time lag for data access and analyses. The database contains disease diagnoses, claims for medical procedures and pharmacy prescriptions (from inpatient and outpatient services in the hospitals covered), and laboratory test results available for approximately 10% of patients. As this study will only use de-identified data, approval from an institutional review board (IRB) will not be necessary for the conduct of this study.

## 8.5. Study Size

From the sales forecast, the number of patients which are “overall” with the following treatment between May 22, 2019 and May 5, 2022 in MDV database is provided below:

- Trelegy 100 treatment: 6450 patients
- MITT treatment: 4370 patients

Considering inclusion and exclusion criteria (refer to “Sec 8.2.1 Inclusion criteria” and “Sec 8.2.2 Exclusion criteria”), the number of patients which are “incident users” is assumed to be from 30% to 50%.

- Trelegy 100 treatment: 1935 to 3225 patients
- MITT treatment: 1311 to 2185 patients

As a result of the phase 3 multinational study (CTT116855) in patients with COPD, the incidence rate of serious pneumonia in Japanese patients with FF/UMEC/VI treatment was 122.8 (/1000 patient-years). Therefore, we assume that incident rate of hospitalization due to CAP for each group within the 360-day follow-up period in this study is 80, 100, 120 or 140 (/1000 patient-years) (follow-up period will be up to 360 days in the base-case analysis).

### 8.5.1. Study Size for HR in primary analysis

In primary analysis, HR for hospitalization due to CAP among incident Trelegy 100 users compared to incident MITT users within the 360-day follow-up period will be estimated along with 95% confidence intervals using Cox proportional hazard model (follow-up period will be up to 360 days in the base-case analysis).

For a relative risk in HR between incident Trelegy 100 users and incident MITT users in real-world data, according to the report, it's stated that "relationships with relative risks varying between 0.5 and 2 are the ones most commonly reported in analyses of real-world data, and are those most susceptible to unaccounted for confounding that can only be addressed with an randomised controlled trials." Also, some key data (ex. lung function test results, respiratory symptoms evaluated by questionnaires and so on) are not available in MDV database, and the difference in the patient characteristics between Trelegy 100 users and MITT users in Japan is not known. Considering these situations, it's reasonable that we won't consider an HR  $\leq$  3 to be a signal.

Given the following combination of sample size, probability of observing HR > 3 is displayed as below. we considered the following patients, as sample size is being projected based on market forecast.

Table 1 Sensitivity based on different hospitalization due to CAP rates, HRs and patients

Incident Trelegy Users	Incident MITT Users	Expected annual hospitalization due to CAP rate (%)	True HR#	Probability of observing HR > 3 (%)
3225	2185	8	2	0.0
			2.5	6.0
			3	50.0
			3.5	88.1
			4	98.2
3225	2185	10	2	0.0
			2.5	4.1
			3	50.0
			3.5	90.7
			4	> 99.0
3225	2185	12	2	0.0
			2.5	2.9
			3	50.0
			3.5	92.6
			4	> 99.0
3225	2185	14	2	0.0
			2.5	2.0
			3	50.0
			3.5	94.1
			4	> 99.0
1935	1311	8	2	0.2
			2.5	11.4
			3	50.0
			3.5	82.0
			4	94.9
1935	1311	10	2	0.1
			2.5	8.9
			3	50.0
			3.5	84.7

			4	96.6
1935	1311	12	2	0.0
			2.5	7.0
			3	50.0
			3.5	86.9
			4	97.7
1935	1311	14	2	0.0
			2.5	5.6
			3	50.0
			3.5	88.7
			4	98.5

Note: Probability of observing HR > 3 using asymptotically normal distribution

### 8.5.2. Study Size for incidence rates in secondary analysis

In secondary analysis, incidence rates for hospitalization due to CAP in Trelegy 100 and MITT groups within the 360-day follow-up period will be calculated along with 95% exact poisson confidence intervals using chi-square distribution (follow-up period will be up to 360 days in the base-case analysis).

The incidence rates of hospitalization due to CAP per 1000 patient-years of follow-up is displayed for different scenarios for each group (Table 2, Table 3, Table4, Table5).

#### 8.5.2.1. Incidence rates of hospitalization due to CAP for overall users

Table 2 Incidence rate of hospitalizations due to CAP (Trelegy 100 group)

Total Patient Years	Number of patients with hospitalizations due to CAP	Incidence rate (/1000 Patient Years)	
		Estimate	95% confidence interval
6450	516	80	[73.25, 87.21]
	645	100	[92.43, 108.02]
	774	120	[111.69, 128.76]
	903	140	[131.02, 149.44]

Note: Exact poisson confidence intervals using chi-square distribution

Table 3 Incidence rate of hospitalizations due to CAP (MITT group)

Total Patient Years	Number of patients with hospitalizations due to CAP	Incidence rate (/1000 Patient Years)	
		Estimate	95% confidence interval
4370	350	80	[71.92, 88.94]
	437	100	[90.84, 109.83]
	524	120	[109.86, 130.63]
	612	140	[129.17, 151.59]

Note: Exact poisson confidence intervals using chi-square distribution

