### Study size

From the sales forecast, the number of patients with the following treatment between May 22, 2019 and May 5, 2022 in MDV database is provided below:

- Trelegy 100 group: 6450 patients
- MITT group: 4370 patients

Considering inclusion and exclusion criteria (refer to “Sec 8.2.1 Inclusion criteria” and “Sec 8.2.2 Exclusion criteria”), the number of patients in this study is assumed to be from 30% to 50%.

- Trelegy 100 treatment: 1935 to 3225 patients
- MITT treatment: 1311 to 2185 patients

In primary analysis, HR for hospitalization due to CAP among incident Trelegy 100 users compared to incident MITT users within the 360-day follow-up period will be estimated along with 95% confidence intervals using Cox proportional hazard model (follow-up period will be up to 360 days in the base-case analysis). Probability of observing  $HR > 3$  is displayed for different scenarios in “Sec 8.5 Study Size”.

In secondary analysis, incidence rates for hospitalization due to CAP in Trelegy 100 and MITT groups within the 360-day follow-up period will be calculated along with 95% exact poisson confidence intervals using chi-square distribution (follow-up period will be up to 360 days in the base-case analysis). The expected 95% confidence intervals for incidence rate of hospitalization due to CAP for different scenarios are described in “Sec 8.5 Study Size”.

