Trelegy 100 is convenient because ICS, LAMA and LABA can be administered simultaneously with one inhalation, and the number of patients prescribed with “triple therapy” may increase compared to the past when only MITT was available. By considering this situation, it makes sense to examine risks for pneumonia in patients treated with Trelegy 100 in real world.

Based on the definition of the follow-up period described in “Sec 8.1 Study Design”, there will be large variation in the observational period among patients. Thus the incidence rate is appropriate for measuring occurrence of pneumonia, and HR is appropriate for comparing the pneumonia occurrence between Trelegy 100 or MITT group.

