**Figure1 Study design**

Identification of the study population will be conducted using health insurance claims data (outpatient and inpatient) and Diagnosis Procedure Combination (DPC) data. Patients surveyed are aged 40 years or older at the start date of prescription (index date) for Trelegy 100 or MITT during the 1,080-day identification period (from May 22, 2019 to May 5, 2022).

In this protocol, one month is defined as 30 days based on the manner of Post-marketing Surveillance in Japan.

In this study, data will be collected retrospectively with the 1,080-day identification period to have as much patient data as possible within the time frame to submit study results for the reexamination application for Trelegy 100. We plan to conduct data review in 2022 as described at the bottom of ABSTRACT, and we need time to agree on the protocol with PMDA after the endorsement by Protocol Review Committee (PRC), and thus we prepared this protocol in 2020.

Patients with records of International Statistical Classification of Diseases and Related Health Problems, Tenth Revision (ICD -10) codes for COPD (J42, J43 or J44), one record at the index date and additional 2 records (outpatient visit or hospital admission) in the 360 days look-back period [index date, index date -360 days]. This criterion is to exclude patients with infrequent visits and to secure collection of patient characteristics data in the look-back period.

At least one record (outpatient visit or hospital admission) with any ICD-10 codes in the 180 days

prior to the start date of look-back period [index date – 360 days, index date – 540 days]. This criterion is to secure patient records throughout the look-back period.

Follow-up period will be from the index date (including the index date) to the earliest date of the followings: 1) admission date of hospitalization due to CAP or 2) date of death or 3) end date of exposure period with Trelegy 100 or MITT by discontinuation (defined in 8.3.1.1. continuation of exposure), or 4) 360 days after the index date.

In base case analysis, the 360-day follow-up period will be applied, while the 1,440-day follow-up period will be used in sensitivity analysis.

The reason for the 360-day follow-up period is based on the article by Suissa et al. which demonstrated that the effect of ICS on pneumonia occurrence among COPD patients peaked in the first year of use.

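### The study-size tables credit every patient with a full year, apply no eligibility loss to overall users, and rest Table 1 on a pooled rate that conflicts with Section 8.5; Tables 2-5 are too precise and Table 1 is unreliable in an unknown direction

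*Protocol*

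**What the plan says.** Section 8.5 takes patient numbers from a sales forecast: "Trelegy 100 treatment: 6450 patients" and "MITT treatment: 4370 patients". Reduced to 30-50%, these give 1935-3225 Trelegy and 1311-2185 MITT patients, whom Section 8.5 calls incident users. The abstract gives the same reduced counts but describes them differently: "the number of patients in this study is assumed to be from 30% to 50" percent, because of the inclusion and exclusion criteria.

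For the event rate, Section 8.5 uses four values from 80 to 140 per 1000 patient-years and makes them per-group rates: "we assume that incident rate of hospitalization due to CAP for each group within the 360-day follow-up period in this study". Their source is a figure of 122.8 per 1000 in Japanese patients on FF/UMEC/VI.

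Two sets of tables follow. "Table 1 Sensitivity based on different hospitalization due to CAP rates, HRs and patients" (Section 8.5.1) gives the probability of observing HR > 3 for one annual rate of 8, 10, 12 or 14%, without naming a group. Tables 2-5 (Section 8.5.2) give exact Poisson intervals for incidence rates, starting with "Table 2 Incidence rate of hospitalizations due to CAP (Trelegy 100 group", which is for overall users.

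On follow-up, Section 8.1 sets a 360-day limit and lists earlier end points, among them "3) end date of exposure period with Trelegy 100 or MITT by discontinuation". Section 7 expects that "there will be large variation in the observational period among patients".

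**The concern.** There are three separate points.

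1. **Person-time.** The total patient-years in Tables 2-5 are 6450, 4370, 3225, 1935, 2185 and 1311, which are exactly the patient counts. Under the Section 8.1 follow-up rule no patient contributes a full year, and those who stop treatment contribute less.
2. **Eligibility.** Section 8.2.1 makes overall and incident users both study populations under the same criteria, yet Tables 2-3 use the unreduced forecast for overall users.
3. **Rate in Table 1.** Section 8.5 assumes 80-140 per 1000 in each group. The largest ratio that range allows is 140/80 = 1.75, while every true HR in Table 1 is 2 or more. No row can keep both groups inside the range.

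These tables are the protocol's only statement of the precision and signal probability the study can offer, and Section 6.2 describes the study as an approval condition. A regulator reading them should be able to tell what they assume.

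**Working it through.** **Reproducing Tables 2-5.** For x events in PY patient-years, the limits are χ²(0.025; 2x)/(2·PY) and χ²(0.975; 2x+2)/(2·PY). With PY set to the number of patients, all 24 intervals match to two decimals. For example, 258 events in 3225 patient-years give [70.54, 90.38] per 1000.

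**Effect of follow-up.** Put PY = patients × mean follow-up and x = PY × rate, rounded. The protocol gives no mean, so 0.7 and 0.5 year are assumptions; 360/365.25 = 0.986 year is the ceiling.

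| Row, at 80 per 1000 | Mean follow-up | PY | Events | 95% CI | Width |
|---|---|---|---|---|---|
| Table 4, 3225 patients | 1 (printed) | 3225 | 258 | [70.54, 90.38] | 19.8 |
| | 0.7 | 2257.5 | 181 | [68.9, 92.7] | 23.8 |
| | 0.5 | 1612.5 | 129 | [66.8, 95.1] | 28.3 |
| Table 5, 1311 patients | 1 (printed) | 1311 | 105 | [65.51, 96.96] | 31.4 |
| | 0.5 | 655.5 | 52 | [59.2, 104.0] | 44.8 |

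At the 0.986 ceiling the first row has 254 events and a width of 20.0 instead of 19.8. The cap alone is therefore negligible; discontinuation drives the loss.

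**Effect of eligibility on Table 2.** The retained fraction for overall users is not stated. If the 30-50% applied to them, with a full year each, the patient-years would be 1935 to 3225. Those intervals are already printed in Table 4: [67.99, 93.75] and [70.54, 90.38]. Table 2 prints [73.25, 87.21], so the width would go from 14.0 to between 19.8 and 25.8.

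**Reproducing Table 1.** P = Φ(ln(HR/3)/SE), with SE = √(1/d_T + 1/d_M). Total events are D = (n_T + n_M) × rate × 1 year, split in the ratio n_T·HR : n_M. For 3225/2185, 8%, HR 3.5:
- D = 5410 × 0.08 = 432.8
- d_T = 432.8 × 11287.5/13472.5 = 362.6 and d_M = 70.2
- SE = 0.1304, z = 0.1542/0.1304 = 1.182, P = 88.1%, as printed

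All 40 cells match this way. Other readings do not. Against the printed 6.0/88.1 at HR 2.5/3.5, splitting events by patient numbers gives 3.1/94.2, putting 8% on Trelegy gives 8.8/84.1, and putting 8% on MITT gives 1.6/96.9.

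**What the pooled rate implies.** At 8% and HR 3, the MITT rate is 432.8/(3225 × 3 + 2185) = 36.5 per 1000 and the Trelegy rate is 109.5. At 14% and HR 4 they are 50.2 and 200.8.

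**Corrected Table 1 probabilities** (3225/2185, 8%):

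| 8% refers to | Follow-up, years | HR 2.5 | HR 3.5 |
|---|---|---|---|
| Both groups pooled (printed) | 1 | 6.0 | 88.1 |
| Both groups pooled | 0.5 | 13.6 | 79.8 |
| Trelegy; MITT = rate/HR | 1 | 8.8 | 84.1 |
| Trelegy; MITT = rate/HR | 0.5 | 16.9 | 76.0 |
| MITT; Trelegy = rate × HR | 1 | 1.6 | 96.9 |
| MITT; Trelegy = rate × HR | 0.5 | 6.5 | 90.6 |

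With the pooled rate kept, the 0.986 ceiling alone moves 88.1 only to 88.0.

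**The case against.** The sponsor can fairly say that this is a retrospective database study taking whatever patients a fixed window provides. The tables set no recruitment target or stopping rule. The final report will show the actual events, person-time and intervals, and Section 8.3.3.2 already plans to tabulate follow-up length. This stands, and it limits the consequence to how the study is presented in advance.

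The sponsor can also say that shorter follow-up acts on Table 1 only through the event count, so it is equivalent to reading a lower-rate row. At a pooled 12% and HR 3.5, 0.7 year gives 88.7% (3225/2185) and 82.6% (1935/1311), close to the printed 8% rows of 88.1% and 82.0%. This is correct, but the protocol does not tell the reader to use the rows that way. It also leaves the conflict over the group rate untouched.

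A reader might go further and infer that Table 1's signal probabilities are too favourable throughout. The documents do not support that. Shorter follow-up with the pooled rate kept does lower the detection probabilities, but placing 8% on MITT raises 88.1% to 96.9%, and even at 0.5 year leaves 90.6%. Against the MITT reading, it implies 80 × 3.5 = 280 per 1000 on Trelegy, well above the cited 122.8, and that figure comes from FF/UMEC/VI patients. This makes a Trelegy anchor more natural but does not settle what was meant. Nor is there a calculation error: every printed figure reproduces, and the fault lies in the assumptions.

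**Conclusion.** The point holds in three parts of different strength.

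- **Tables 2-5** overstate precision, because one full year per patient is impossible under Section 8.1. How much depends on an unstated mean follow-up: intervals are about 20% wider at 0.7 year and about 42% wider at 0.5 year for the 3225-patient row at 80 per 1000 (23.8/19.8 and 28.3/19.8).
- **Tables 2-3** also apply no eligibility loss, and the abstract and Section 8.5 conflict on what the 30-50% describes. The size of the loss for overall users cannot be derived from the protocol. This part does not touch Table 1, which uses incident users.
- **Table 1** contradicts the per-group rate in Section 8.5 and assumes a full year per patient. Its probabilities are unreliable, but whether they are too high or too low depends on which group the rate belongs to and on follow-up.

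This should be corrected, since the tables are the only prospective account of what the study can show. It does not invalidate the planned analysis.

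**What to change.** Recompute Tables 1-5 with patient-years equal to eligible patients times an assumed mean on-treatment follow-up, shown over a range such as 0.5, 0.7 and the 0.986-year maximum. In Table 1, name the group to which the annual rate refers and derive the other group's rate through the HR. Make the abstract and Section 8.5 agree on whether the 30-50% covers all study patients or incident users only, and apply a stated eligibility fraction to overall users in Tables 2-3. Then restate the intervals and probabilities.

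The cost is a recalculation and a text amendment, with no extra patients or data. The intervals in Tables 2-5 will widen; the Table 1 probabilities may move either way.
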